6.3 Lifestyle Restrictions

Not applicable. No restrictions are required

6.4 Screen Failures

Screen failures are defined as participants who consent to participate in the clinical study but who are not subsequently randomized in the study/included in the analysis population. A minimal set of screen failure information is required to ensure transparent reporting of screen failure participants, to meet the Consolidated Standards of Reporting Trials (CONSORT) publishing requirements, as applicable, and to respond to queries from regulatory authorities. Minimal information includes date of consent, demography, screen failure details, eligibility criteria, and any serious AEs.

6.4.1 Retesting During Screening Period

Participant Re-enrollment: This study permits the re-enrollment of a participant that has discontinued the study as a screen failure (ie, participant has not been randomized). If re-enrolled, the participant must be re-consented.

Retesting of laboratory parameters and/or other assessments within any single Screening Period will be permitted (in addition to any parameters that require a confirmatory value).

The most current result prior to Randomization is the value by which study inclusion will be assessed, as it represents the participant's most current, clinical state.

Laboratory parameters and/or assessments that are included in [Table 2-1](#) (Screening Procedural Outline) may be repeated in an effort to find all possible well-qualified participants. Consultation with the Medical Monitor may be needed to identify whether repeat testing of any particular parameter is clinically relevant.

Testing for asymptomatic COVID-19, for example by reverse transcription polymerase chain reaction (RT-PCR) or viral antigen, is not required. However, some participants may develop suspected or confirmed symptomatic COVID-19 or be discovered to have asymptomatic COVID-19 during the screening period. In such cases, participants may be considered eligible for

the study after meeting all inclusion/exclusion criteria related to symptomatic infection and after meeting the following criteria:

- At least 10 days (20 days for severe/critical illness) have passed since symptoms first appeared or positive RT-PCR or viral antigen test result, and
- At least 24 hours have passed since last fever without the use of fever-reducing medications, and
- Acute symptoms (eg, cough, shortness of breath) have resolved, and
- In the opinion of the Investigator and in consultation with the Medical Monitor or Clinical Scientist, there are no COVID-19-related sequelae (eg, cardiovascular) that may place the participant at a higher risk of receiving investigational treatment, and
- Negative follow-up SARS-CoV-2 RT-PCR or viral antigen test based on institutional, local, or regional guidelines.

7 TREATMENT

Study treatment is defined as any investigational treatment(s), marketed product(s), placebo or medical device intended to be administered to a study participant according to the study randomization or treatment allocation.

Study treatment includes both Investigational [Medicinal] Product (IP/IMP) and Non-investigational [Medicinal] Product (Non-IP/Non-IMP) and can consist of the following:

- Nivolumab
- Relatlimab

An IP, also known as IMP in some regions, is defined as a pharmaceutical form of an active substance or placebo being tested or used as a reference in a clinical study, including products already with a marketing authorization but used or assembled (formulated or packaged) differently than the authorized form, or used for an unauthorized indication, or when used to gain further information about the authorized form.

Other medications used as support or escape medication for preventative, diagnostic, or therapeutic reasons, as components of the standard of care for a given diagnosis, may be considered as non-IPs.

IPs used in this trial are provided in [Table 7-1](#). There are no non-IPs in this study.

Table 7-1: Study Treatments for CA224073

Product Description/ Class and Dosage Form	Potency	IP/Non-IMP	Blinded or Open Label	Packaging/Appearance	Storage Conditions (per label)
Relatlimab ^a Injection (10 mg/mL)	10 mg/mL	IP	Open-label, 4 vials per carton/ 80 mg/vial (8 mL vial)	Colorless to pale yellow liquid, clear to opalescent, light (few) particulates (consistent in appearance to protein particulates) may be present.	Refer to the label on container and/or Pharmacy Manual.
Nivolumab ^a Injection (10 mg/mL)	10 mg/mL	IP	Open-label, 4 vials per carton/ 100 mg/vial (10 mL vial)	Clear to opalescent, colorless to pale yellow liquid. Light (few) particulates may be present.	Refer to the label on container and/or Pharmacy Manual.

Abbreviations: IMP = investigational medicinal product; IP = investigational product; mg = milligram; mL = milliliter.

^a Relatlimab is sometimes referred to as BMS-986016; Nivolumab is sometimes referred to as BMS-936558.

7.1 Treatments Administered

The selection and timing of dose for each participant is provided in Table 7.1-1.

Table 7.1-1: Treatments Administered

Study Arm	Study Treatment	Dose Level	Frequency of Administration and Duration of Treatment	Route of Administration	Approximate Infusion Time, minutes
Arm A	Nivolumab	480 mg	Q4W Until progression, unacceptable toxicity, or withdrawal of consent	IV	30
Arm B	Nivolumab/ Relatlimab ^a	480 mg/ 480 mg	Q4W Until progression, unacceptable toxicity, or withdrawal of consent	IV	60
Arm C	Nivolumab/ Relatlimab ^a	480 mg/ 960 mg	Q4W Until progression, unacceptable toxicity, or withdrawal of consent	IV	60 ^b

Abbreviations: IV = intravenous; mg = milligram; Q4W = every 4 weeks.

^a Nivolumab and relatlimab are co-administered.

^b Infusions will occur over approximately 60 minutes for participants weighing equal to or greater than 45 kg, and for participants weighing less than 45 kg, infusions will occur over approximately 90 minutes.

7.1.1 Relatlimab Combined with Nivolumab Dosing

Relatlimab and nivolumab will be administered on Day 1 of each Q4W treatment cycle. For Q4W dosing cycles, participants may be dosed no less than 26 days from the previous dose.

Participants should be carefully monitored for infusion reactions during administration. If an acute infusion reaction is noted, the participant should be managed according to [Section 7.4.4](#).

Participants should receive relatlimab and nivolumab until progression, unacceptable toxicity, withdrawal of consent/assent by the participant, or the study ends, whichever occurs first.

There will be no dose escalations or reductions of relatlimab or nivolumab. Premedication for potential infusion reaction is not recommended for the first dose of either treatment.

Doses of relatlimab or nivolumab may be interrupted, delayed, or discontinued depending on how well the participant tolerates the treatment. Dosing visits must not be skipped, only delayed. See [Section 7.4](#) (Dosage Modification) and [Section 8.1](#) (Discontinuation from Study Treatment).

The relatlimab and nivolumab injections can be infused undiluted or diluted. The infusion must be promptly followed by a flush of diluent to clear the line. Instructions for dilution and infusion of relatlimab and nivolumab injections will be provided in the Pharmacy Manual. Care must be taken to assure sterility of the prepared solution as the product does not contain any antimicrobial preservative or bacteriostatic agent.

For details on prepared drug storage, preparation, and administration, please refer to the IBs^{8,36} and/or Pharmacy Manual. The selection and timing of dose for each participant is provided in [Table 7.1-1](#).

For the 960-mg relatlimab/480-mg nivolumab dose, infusions will occur over approximately 60 minutes for participants weighing equal to or greater than 45 kg, and for participants weighing less than 45 kg, infusions will occur over approximately 90 minutes.

Study treatment will be dispensed by IRT at the study visits as listed in [Section 2](#) (Schedule of Activities).

7.1.2 Best Supportive Care

Recommendations for best supportive care (BSC) can be found in the European Association for the Study of the Liver (EASL) Clinical Practice Guidelines: Management of HCC.⁶⁴ These include up to 3 g/day acetaminophen (paracetamol) for management of mild pain. Nonsteroidal anti-inflammatory medications should be avoided in participants with cirrhosis. Pain of intermediate or severe intensity can be managed with opioids, with care taken to avoid opioid-induced constipation.

7.1.3 Palliative Therapy

Palliative local therapy for clinically symptomatic tumor sites (ie, for pain, bleeding, spinal cord compression, brain metastasis, new or impending pathologic fracture, superior vena-cava syndrome, or obstruction) including palliative (limited-field) radiation and palliative surgical resection may be considered during trial therapy if the following criteria are met:

- The participant is considered to have progressed at the time of palliative therapy and meets criteria to continue with treatment beyond progression.
- OR
- The lesion for palliative local therapy is a non-target lesion which has not met criteria for progression.
- Tumor lesions requiring palliative local therapy should be evaluated for objective evidence of disease progression prior to the initiation of such therapy. The potential for overlapping toxicities with radiotherapy and nivolumab/nivolumab plus relatlimab currently is not known; however, anecdotal data suggest that radiotherapy with nivolumab is tolerable. If palliative radiotherapy is required, then study drugs should be withheld for at least 1 week before, during, and 1 week after radiation. Palliative therapy must be clearly documented in the source records and case report form (CRF). Details in the source records should include dates of treatment, anatomical site, dose administered and fractionation schedule, and AEs.

7.2 Method of Treatment Assignment

Study treatment will be dispensed at the study visits as listed in [Section 2](#) (Schedule of Activities). Before the study is initiated, each user will receive login information and instructions on how to access the IRT. After the participant's ICF has been obtained and initial eligibility is established, the participant must be enrolled into the study by using IRT to obtain the participant number. Every

participant who signs the ICF must be assigned a participant number in IRT. The Investigator or designee will register the participant for enrollment by following the enrollment procedures established by BMS. All procedures will be clarified in the IRT manual.

Study treatment will be dispensed at the study visits per the [Section 2](#) (Schedule of Activities). During the screening visit, the investigative site will call into the enrollment option of the IRT designated by BMS for assignment of a 5-digit participant number that will be unique across all sites. Enrolled participants, including those not dosed, will be assigned sequential participant numbers starting with [REDACTED]. The participant identification (PID) number will ultimately be comprised of the site number and participant number. For example, the first participant screened (ie, enrolled) at site number 1, will have a PID of [REDACTED]. Once it is determined that the participant meets the eligibility criteria following the screening visit, the investigative site will call the IRT to assign the participant into the open dose level.

Treatment assignments for eligible participants will alternate among the arms, with screened participants assigned to different parts through IRT. If a treatment arm becomes overly enrolled because of screen failures in alternate arms, it can be temporarily closed to allow enrollment in the other arms. Once balance is achieved, the temporary hold can be lifted. If there are no openings available in the part to which the participant would be assigned by this algorithm, the participant will be assigned to the next open part/cohort until respective dose levels or cohorts have completed accrual according to principles outlined in [Section 5.1.2](#) (Treatment Period).

[figure not shown]
Participants will not be replaced if they are discontinued from the study secondary to an AE unless the AE can be determined to be unrelated to treatment.

[figure not shown]

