Revised Protocol 01	28-Oct-2020	The primary reasons for these changes are to align dose modification criteria [REDACTED] with the current Common Terminology Criteria for Adverse Event (CTCAE) version (v5); add serologic testing for severe acute respiratory syndrome coronavirus 2 (SARS-CoV-2) status; and incorporate additional updates to improve alignment across protocol sections and/or clarify expectations for eligibility, assessments, sample collections, treatment administration, and country-specific requirements.
Original Protocol	29-May-2020	Not applicable

OVERALL RATIONALE FOR PROTOCOL AMENDMENT 04:

[figure not shown]
[figure not shown]
The primary rationale for Protocol Amendment 04 is to make overall study design changes and clarify several items throughout the protocol.

[figure not shown]
The original design of CA224-073 was a 3-arm study randomized 2:1:2 with the following treatment arms:

- Arm A: nivolumab 480 mg every 4 weeks (Q4W)
- Arm B: nivolumab 480 mg Q4W + relatlimab 480 mg Q4W
- Arm C: nivolumab 480 mg + relatlimab 960 mg Q4W

24 participants were randomized in Arm C.

[figure not shown]
SUMMARY OF KEY CHANGES FOR PROTOCOL AMENDMENT 04		
Section Number & Title	Description of Change	Brief Rationale
Title page	Changed Medical Monitor from [REDACTED], to [REDACTED], Clinical Scientist from [REDACTED] to [REDACTED], and their associated contact information.	To report important personnel changes.
Table 2-1: Screening Procedural Outline (CA224073)	Removed the following text from notes corresponding to the “Pre-screening for Tumor Tissue Sample” row: “All other procedures may be performed within 14 days if pre-screening ICF is used.”	To avoid confusion regarding procedures that can be done with pre-screening informed consent form (ICF).
	Modified the language from “Most” to “All” inclusion/exclusion criteria in notes corresponding to the Inclusion/Exclusion Criteria row.	For clarity.

SUMMARY OF KEY CHANGES FOR PROTOCOL AMENDMENT 04		
Section Number & Title	Description of Change	Brief Rationale
	Added the following text to notes corresponding to the row Physical Examination: “Full physical examination including height, weight, and BMI. Any findings during the PE will be recorded as medical history in the participant’s medical records and on the appropriate CRF.”	Clarified requirements for physical examination.
	Oxygen saturation was added to vital sign assessments.	Clarified requirements for vital sign assessments.

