Abbreviations: AE = adverse event; BICR = Blinded Independent Central Review; DCR = disease control rate; DOR = duration of response; HCC = hepatocellular carcinoma; IO = immuno-oncology; ORR = objective response rate; OS = overall survival; PFS = progression-free survival; RECIST = Response Evaluation Criteria in Solid Tumors; SAE = serious adverse event; TKI = tyrosine kinase inhibitor.

Overall Design:

This Phase 2 study will evaluate the safety and efficacy of relatlimab in combination with nivolumab in participants with 2L or 3L IO-naive HCC.

[figure not shown]
As of 19-July-2021, participants are being randomized 1:1 to receive:

[figure not shown]
- Arm A:** Nivolumab 480 mg Q4W
- Arm B:** Nivolumab 480 mg Q4W+ Relatlimab **480** mg Q4W

- [REDACTED]

Arm C: Nivolumab 480 mg Q4W+ Relatlimab **960** mg Q4W

[REDACTED] 24 participants were randomized to Arm C.

For Protocol Amendment 03, all participants in Arm B and Arm C were re-consented. All new participants at the time had signed the updated informed consent for Protocol Amendment 03.

This is an open-label, randomized Phase 2 study in adult (≥ 18 years) male and female participants with advanced, Child-Pugh A, IO-naive HCC who have experienced progression that was demonstrated radiographically on or after one or two prior TKI therapies in the advanced/metastatic setting. Participants must not be amenable for management with surgery or locoregional therapy or have progressed after surgery or locoregional therapy.

Stratification will occur by region (Asia [excluding Japan] vs Rest of the World [including Japan]) and macrovascular invasion and/or extrahepatic spread (MVI/EHS; present or absent). For the purposes of randomization, LAG-3 will also be treated as a stratification factor.

MVI is defined as:

- Hepatic vein tumor thrombus, OR
- Inferior vena cava tumor thrombus, OR

- Portal vein tumor thrombus; Vp3/Vp4 (presence of a tumor thrombus in the main trunk of the portal vein or a portal vein branch contralateral to the primarily involved lobe or first-order branches of the portal vein) participants are also eligible.

EHS is defined as presence of metastatic disease in lymph nodes or distant sites outside the liver.

[figure not shown]

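### Section 7.2 describes allocation by alternation, with arm-closure and next-open-cohort rules, which contradicts the stratified randomisation stated in the rest of the protocol

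*Combined protocol and SAP*

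**What the plan says.** Section 7.2 (Method of Treatment Assignment) sets out four linked rules in its visible text.

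- The first concerns the assignment call. After a participant is found eligible, the site contacts the IRT, which places that person in whichever dose level is open.
- The second is the rule for choosing the arm, worded as follows: "Treatment assignments for eligible participants will alternate among the arms, with screened participants assigned to different parts through IRT".
- The third allows a pause in accrual to one arm, and gives the reason for it: "If a treatment arm becomes overly enrolled because of screen failures in alternate arms, it can be temporarily closed". The hold is lifted once balance returns.
- The fourth covers the case where the algorithm finds no opening. Then "the participant will be assigned to the next open part/cohort until respective dose levels or cohorts have completed accrual". For the governing principles the sentence points to Section 5.1.2.

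Elsewhere the protocol describes something different.

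- Synopsis, Overall Design: "As of 19-July-2021, participants are being randomized 1:1 to receive" Arm A or Arm B. Stratification is by region and by MVI/EHS, and "For the purposes of randomization, LAG-3 will also be treated as a stratification factor".
- Overall rationale for Amendment 04: "The original design of CA224-073 was a 3-arm study randomized 2:1:2".
- Table 2-2 has the site contact the IRT to randomise the participant, only after eligibility is confirmed.
- Section 5.1.2 opens the treatment phase with a randomisation call to the IRT and says assignment to the two arms is random.
- Section 5.4.4 lists the three stratification factors, and Section 9.8.2.2 repeats that LAG-3 status is one of them.
- Section 7.3 calls the study randomised and open label to sponsor and site.

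**The concern.** Alternation is a deterministic rule. It is not a loose way of describing stratified randomisation: under alternation the next arm follows from the previous one, and under randomisation it does not. Temporarily closing an arm, or diverting a participant to whichever cohort is open, also departs from a stratified randomisation schedule.

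This matters because of what rests on the allocation. The primary result is the difference in BICR-assessed ORR between Arm B and Arm A, analysed on the randomised population (Section 10.3.1). Blinded central review protects the reading of scans. It does not protect the decision about which patient enters, or when, if someone at the site can anticipate the next arm. In an open-label trial, random and concealed allocation is the main safeguard against that. A reader or inspector who goes to the section headed as the method of assignment finds a rule that does not provide it, and cannot tell from the protocol which rule governed.

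**Working it through.** No arithmetic applies, because the conflict is one of wording. The check sets the statements side by side.

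1. **How the arm is chosen.** Section 7.2: by alternating among arms. Synopsis, Table 2-2, and Sections 5.1.2 and 7.3: by randomisation. The IRT is common to both descriptions, so naming the IRT does not reconcile them. The question is what rule the IRT applies.

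2. **Ratio and strata.** The Synopsis gives 1:1 as of 19-July-2021, and the Amendment 04 rationale gives 2:1:2 for the original three arms. The Synopsis and Sections 5.4.4 and 9.8.2.2 give the stratification. The visible text of Section 7.2 mentions neither. That section contains places where a figure is not shown, so nothing can be said about what may stand there.

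3. **The cross-reference.** Section 7.2 sends the reader to Section 5.1.2 for the principles behind its algorithm. Section 5.1.2 contains no alternation, closure or next-open rule; it says assignment is random. The reference therefore leads to text that contradicts the sentence citing it.

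4. **The closure trigger.** Section 7.2 lets an arm close because of screen failures in other arms. Section 6.4 defines screen failures as people who consented but were not randomised, so they belong to no arm. Table 2-2 places randomisation after eligibility is confirmed, and Section 7.2 itself places the IRT assignment call after eligibility is determined. The event that triggers the closure cannot arise under this design.

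5. **Vocabulary.** The visible text describes two open arms, with Arm C no longer receiving participants. It describes no parts or cohorts accruing in sequence. Those words suggest text carried over from a cohort design. That is an inference; the documents do not say so.

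Statements 1, 3 and 4 are each enough to show that Section 7.2 cannot stand beside the rest of the protocol. Statement 5 only suggests how the text came to be there.

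**The case against.** The strongest reply is that this is a drafting inconsistency with no demonstrated effect. Every other relevant section says the trial is randomised, assignment goes through the IRT on either description, and an IRT manual, to which Section 7.2 refers procedures, may hold the correct rule. Some of the wording is also less foreign than it looks: dose level is a column heading for the arms in Tables 1-2 and 7.1-1, and closing or dropping an arm is contemplated in Sections 3.3.3 and 10.3.1, though not temporary closure for over-enrolment. All of this stands. It limits the consequence but does not remove the contradiction, since a correct manual would not correct the protocol.

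Two stronger readings are tempting and should be resisted.

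- A reader might infer that the documents' own numbers disprove Section 7.2, because equal alternation among three arms gives 1:1:1 and not 2:1:2. The only arm count given is for Arm C: "24 participants were randomized in Arm C". With 24 in Arm C, a 2:1:2 ratio implies 24 x 2/2 = 24 in Arm A and 24 x 1/2 = 12 in Arm B, while equal alternation implies about 24 in each. The schemes differ only in Arm B, and early counts for Arm B are not given. A fixed repeating sequence such as A-C-B-A-C would also yield 2:1:2. Any expected inequality in final A and B sizes would come from the disclosed change of ratio, not from Section 7.2.
- A reader might infer that allocation was in fact predictable and the primary comparison biased. Section 7.3 says treatment is not masked. It does not say that a site sees other sites' assignments, and the list structure is not given. Nothing shows that alternation was implemented.

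**Conclusion.** The point holds as an internal contradiction: Section 7.2 is wrong as written and should be corrected. It is a wrong rule in the section that defines allocation, which is more serious than a missing detail or a slip in background text. Followed literally, it would give deterministic, non-stratified allocation for the primary Arm B versus Arm A comparison.

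No size is attached. The documents give no evidence that any participant was alternated, that an arm was closed under this rule, or that ORR is affected. The conclusion rests only on the visible current text of the sections named. Hidden text in Section 7.2 could add a ratio or the strata, but it could not make a statement that assignments alternate agree with random assignment.

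**What to change.** 1. Confirm from the IRT specification and the allocation records what rule was actually implemented, before and after 19-July-2021.
2. Delete from Section 7.2 the sentences on alternation and temporary arm closure, and those on open dose levels, parts and cohorts.
3. State in their place that participants are randomised through the IRT, stratified by region, MVI/EHS and LAG-3, 1:1 to Arms A and B as of 19-July-2021 and 2:1:2 across Arms A, B and C under the original design. Align this with Sections 5.1.2 and 5.4.4.
4. Only if the records show that a participant was alternated or redirected under the Section 7.2 rule, report that with the primary comparison.

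The cost is one records check and a protocol wording change. It needs no additional participants or procedures.
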